1.0 BACKGROUND AND RATIONALE

1.1 Study Synopsis

This study will evaluate the content validity of using a survey to quantify patient preferences at the point-of-care for newly-diagnosed patients with hematologic malignancies. Our primary hypothesis is that by identifying the strength of patient preferences for outcomes with this survey, clinicians will be able to improve goal-concordant care by aligning clinical recommendations with patients' preferences. We will conduct cognitive interviews with 20 patients to establish the content validity of the survey. We will use purposive sampling based on the results of the survey to create two groups of patients (n=10 each) for the cognitive interviews. We plan to recruit 50 total patients to complete the survey to ensure adequate recruitment in each group. Secondary outcomes will evaluate acceptability and feasibility of administering the survey. The information we obtain from these participants will be used to refine the survey. Interviews with oncologists and palliative care specialists (up to 10) will inform implementation.

1.2 Background

Treatment decisions in oncology are increasingly preference sensitive. Cancer patients differ substantially in their preferences for achieving various outcomes.¹⁻³ For example in AML, we have shown that some patients prefer to maximize their overall chance of long-term survival and are willing to endure a high burden of side effects or a lengthy hospitalization for this opportunity; others prefer to minimize treatment effects in order to maintain their quality of life.¹ As more therapies are becoming available across oncology, this preference heterogeneity suggests that treatment decisions will increasingly become preference sensitive—ideal therapy choice will depend on patients' preferences for treatment outcomes.

Routine shared decision-making (SDM) is currently inadequate to reliably capture patient preferences.⁴⁻⁸ Multiple systematic reviews have demonstrated consistent discordance after routine SDM between physician perceptions of what matters most to patients and patients' stated preferences.^{8,9} A recent evaluation of a clearly preference-sensitive decision in oncology demonstrated that about half the time oncologists did not elicit patient preferences.¹⁰ Analyses of the quality of SDM in leukemia, for example, demonstrate a high rate of patient dissatisfaction with communication and very poor patient-provider concordance on goals and prognosis.¹¹⁻¹³ As a stark example of patient-provider discordance following routine SDM, 80% of leukemia patients receiving symptom-directed therapy believe they are likely to be cured, when less than 5% will be.¹⁴ Palliative care clinicians can serve to improve these outcomes, but often have limited bandwidth to see most patients.

Preference elicitation instruments can capture patient preferences, however fundamental challenges remain to their implementation in complex clinical care. Numerous stakeholders including the FDA strongly advocate for patient

preferences to be integrated into SDM and clinical care.¹⁵⁻¹⁸ Preference elicitation instruments that were originally developed in economics to understand consumer behavior are increasingly being applied in healthcare to identify outcomes that are most valued by stakeholders. These instruments allow researchers to understand the relative importance of a group of items (attributes) to a population based on a series of choice tasks.¹⁹⁻²¹ In clinical trials evaluating dichotomized decisions where the risks and benefits of treatment options are well-established, these instruments have been shown to improve patient satisfaction, increase high-quality decisions, and align treatment choice with risk.^{2,22-25} Fundamental questions remain, however, about how to assess and apply preference data to complex SDM in advanced cancer patients where risks and benefits of available options vary for each patient.²⁶⁻²⁸ Further, substantial methodological barriers exist in assessing individual preferences over time and pose a critical challenge to longitudinal goal-concordant care. To address these critical gaps, we will use treatment decisions for patients with hematologic malignancies as the context for developing generalizable strategies to improve the goal-concordance of complex treatment decisions in palliative care/oncology.

1.3 Purpose and Rationale

In this study, we will recruit older (≥ 60 years) participants with newly-diagnosed hematologic malignancies to complete the BWS survey and provide quantitative and qualitative feedback to validate the survey. Interviews with a sample of oncologists and palliative care physicians will be completed to identify barriers and facilitators to implementation of the survey into routine clinical care.

2.0 STUDY OBJECTIVES AND ENDPOINTS

2.1 Primary Objective

To evaluate the content validity of using a BWS survey to quantify the preferences of older patients with hematologic malignancies at the point-of-care.

Content Validity: Content validity will be assessed in cognitive interviews with participants. We will first assess the respondent's comprehension of the questionnaire and its items in relation to their intended meaning. We will identify any formatting or wording difficulties with the survey itself. Next, we will evaluate participants comprehension of the content by use of probing questions to evaluate if other important aspects of treatment decision-making were absent in the survey.

2.2 Secondary Objectives

1. To report the acceptability of the BWS survey to patients. This will be defined as participants answering agree/strongly agree to "I found the survey acceptable to clarify my preferences".

2. To report the preliminary efficacy of the BWS survey to improve goal-concordant care. This will be defined as participants answering “moderately effective/very effective” to the question: “How effective was the survey to help you and your doctor choose a treatment that was consistent with your goals?”
3. To report on completion rate over time. This will be reported by the number of patients who complete the BWS survey at each timepoint across the study.

2.3 Exploratory Objectives

1. [REDACTED]

[REDACTED]

[REDACTED]

[REDACTED]

3.0 PARTICIPANT ELIGIBILITY

3.1 Inclusion Criteria

Patients must meet all of the inclusion criteria listed below to participate in the study.

- have a confirmed new diagnosis of the following hematologic malignancies:
 - Aggressive lymphoma (including, but not exclusive of, diffuse large B-cell lymphoma, advanced stage Hodgkin’s lymphoma, Burkitt lymphoma, double hit lymphoma, mantle cell lymphoma)
 - multiple myeloma
 - chronic lymphocytic leukemia
 - chronic myeloid leukemia
 - acute myeloid leukemia
 - acute lymphoblastic leukemia
 - myelodysplastic syndrome with excess blasts (MDS EB1 or MDS EB2)
- Age ≥ 60
- Ability to read, understand, and communicate fluently in English
- Ability to understand and comply with study procedures

- Willingness and ability to provide written informed consent

Patients will become eligible for enrollment upon pathologic confirmation.

Patients will be eligible for enrollment for 28 days after confirmatory diagnosis or until the start of chemotherapy.

Chemotherapy will not include hydroxyurea, cyclophosphamide, or cytarabine if used only for emergent cytoreduction.

Health care clinicians must be employed in hematology/oncology or palliative care as a nurse navigator, advanced practitioner, and/or physician. Together, these participants will be referred to as healthcare clinicians.

3.2 Exclusion Criteria

All subjects meeting any of the exclusion criteria listed below at baseline will be excluded from study participation:

- 3.2.1 Dementia, altered mental status, or psychiatric condition that would prohibit the understanding or rendering of informed consent or participation in the discrete choice experiment.
- 3.2.2 Significant medical conditions, as assessed by the investigators, that would substantially increase the burden on the patient to complete study assessments (such as multiorgan failure, respiratory failure, or other critical illness).

4.0 STUDY PLAN

4.1 Schema

- 4.1.1 This study will evaluate the validity of using this out(BWS) survey to quantify patient preferences at the point-of-care and the potential effectiveness of the survey to improve goal-concordant care. Our primary hypothesis is that by identifying the strength of patient preferences for outcomes with this survey, clinicians will be able to improve goal-concordant care by aligning clinical recommendations with patients' preferences.

Within this study we aim to evaluate the content validity, acceptability, and potential effectiveness of the BWS survey to improve goal-concordant care. Using the BWS survey, we will collect the preferences of 50 older (>60 years) newly-diagnosed hematologic cancer patients facing treatment decisions and evaluate content and construct validity of the survey, patient acceptability, and

effect of preference elicitation on patient-reported quality of treatment decisions (effectiveness). Qualitative interviews involving cognitive interview questions (n=20) with patients will further explore the content validity of the survey and potential effect of the surveys on goal-concordant care. Interviews with palliative care clinicians, and oncologists will explore barriers and facilitators of implementation.

We also aim to describe how patients' preferences change over time and explore potential relationships between patients' preferences and clinical outcomes. We will collect the preferences of the patients with hematologic cancer every other week for 3 months (repeat sampling up 5 times) and then every 3 months thereafter for up to 2 years. We will describe changes in preferences at each timepoint. An exploratory, hypothesis-generating analysis will evaluate correlations between preferences and standard clinical outcomes (e.g. treatment intensity and response), symptoms (collected with the PRO-CTCAE), health-related quality of life (EQ-5D), and decisional satisfaction to provide direction for future studies.

4.1.2 Trial Schema outline (patients)

Clinical Timeline:	New Diagnosis	Clinic Visit: Treatment Decision	Within 14 days of treatment decision	3 months after treatment decision	Every 2 weeks after LA 1	Every 3 months after LA 1
Study Activity:	Enrollment, Complete BWS, Baseline Questionnaire	Longitudinal Assessment (LA) 1: BWS, Follow-up Questionnaire	Cognitive and Qualitative Interview	Cognitive and Qualitative Interview	Longitudinal Assessments 2 - 6	Extended Assessments 1 - 7
Domains assessed:	Baseline Preferences, HRQoL, Symptoms, Decisional Conflict	Acceptability, Prelim efficacy, Preferences, Communication, Decision Regret, Follow-up domains	Content validity	Content validity	Preferences, Communication, Decision Regret, Follow-up domains	Preferences, Communication, Decision Regret, Follow-up domains

4.2 Duration of Study

The recruitment is planned to last for up to 24 months. Patients will complete the survey instruments up to 6 times over 3 months (Longitudinal Assessments) and then every 3 months for up to 2 years (7 times) (Extended Assessments). Patients will complete qualitative interviews within 3 months of treatment decision. Clinicians will be interviewed once over the course of the study.

4.3 Study Details

4.3.1 The study will recruit 50 total participants and conduct qualitative interviews on a subset of 20 participants.

4.3.2 **Pilot testing:** The study team will review the inpatient census and clinic schedule to evaluate for potentially eligible patients. The study team will confirm patient eligibility with the primary oncologist or principal investigator. Eligible patients will be sequentially approached to be recruited to this study until 50 patients are recruited who complete BWS survey.

Upon enrollment, the study team will record information about patients obtained from the patient or the medical record including gender, age, lab values including complete metabolic profile, complete and differentiated blood counts, albumin, LDH, a1c, cholesterol levels, hematopathology reports, clinician-determined performance status (Karnofsky and ECOG), and comorbidities present.

Demographic information such as age, sex, and zip code will be obtained.

Once consented, patients will complete initial study questionnaires within PRO Core either remotely if able or in-person with the assistance of study staff prior to a clinic visit. For patients who decline to participate in the study, reasons for refusal will be anonymously collected to examine the issue of selection bias as well as to assist with determination of feasibility.

After the clinic visit, patients will be prompted to complete the first longitudinal assessment via PRO Core. This will be available for 7 days. The treating oncologist who saw the patient will be prompted to fill out an assessment via email. Clinicians may receive multiple reminder emails to complete the survey to improve completion rates. We will collect provider responses within 2 weeks of initial patient survey.

Following, every 2 weeks (up to 5 times) participants will be prompted in PRO Core to complete the longitudinal assessment survey. Then, the extended assessment survey will be delivered by PRO Core every 3 months for up to 2 years (7 times).

Retention:

Multiple strategies will be utilized to retain patients on study.

1. *Provide Detailed Rationale of the Study and Study Brochure:* Upon enrollment participants will be informed of the rationale of the study: to help understand what is most important to each patient to tailor therapy to patient preferences. Patients will be informed that their responses will help adapt the survey that they will receive to help future patients. They will be given printed information about the study if recruitment is done in person.

2. *Training:* Each patient will receive training on how to complete the assessments in PRO Core. This will take place during enrollment (either in person or remotely).
3. *Reminders to complete the initial post-visit assessments:* The day after the treatment encounter, patients will receive an automated reminder to complete the assessments.
4. *Reminders to complete the follow-up assessments:* Staff will direct them to complete the assessment remotely via a secure link sent by email. PRO Core will send patients a reminder daily for up to 2 days in case of non-response. Study staff will call patients if no response.
5. *Reminders in case of non-response:* Study staff will call patients if no response.
6. *Support to complete assessments:* Staff will assist participants to log-on to PRO Core and to complete assessments if needed.
7. *Compensation:* Participants will be provided with a \$10 gift card following completion of each longitudinal and extended assessment.

4.3.3 **Qualitative Interviews:** Based on responses to the survey, 20 patients will be selected to complete interviews. Patients will complete an initial interview and a follow-up interview.

The study team will review patients who have consented to the study and confirm eligibility with the primary oncologist or principal investigator. Study staff will call eligible patients to participate in the interviews until the number of desired participants has been reached (n=20) according to the inclusion criteria above and recruitment goals below.

We will use purposive sampling to stratify participants based on the results of the BWS survey. We will stratify into two groups of 10 participants each:

1. Those participants who believe that “Living longer” is the most important attribute,

and

2. Those participants who believe another attribute is the most important attribute.

Staff will setup a time to interview eligible participants. Interviews will be scheduled within 14 days of the treatment decision (+ 14 days). A reminder email and/or phone call will be sent to participants the day before and the day of the interview. If participants do not respond during the pre-scheduled time, staff will reschedule the interview/reminders. Participants will be provided with a \$25 gift card following completion of the interview.

Follow-up interviews will be around 3 months after the initial interview (+ 30 days). Interviews will follow the same format as the initial interview. Participants will be provided with a \$25 gift card following completion of the interview.

Interviews will also be completed with up to 5 oncology clinicians and up to 5 palliative care clinicians. Clinicians will be referred to the study staff by the principal investigator. Interviews will take place over the course of 1 year and will not be time dependent upon patient enrollment. Participants will be provided with a \$25 gift card following completion of the interview.

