5.0 TIME AND EVENTS TABLE

5.1 Time and Events Table

	Study Enrollment	Interim	Longitudinal/ Extended assessments	Qualitative Interviews
Screening	X			
Informed Consent	X			
HIPAA	X			
Enrollment Questions	X			
Decision Self-Efficacy	X			
Values subscale of DCS	X	X (if not completed at enrollment)	X	
BWS	X	X (if not completed at enrollment)	X	X
Baseline Questionnaire	X	X (if not completed at enrollment)		
PROMIS cognitive function	X	X (if not completed at enrollment)		
EQ-5D-5L	X	X (if not completed at enrollment)	X	
PRO-CTCAE	X	X (if not completed at enrollment)	X	
PROMIS emotional distress	X	X (if not completed at enrollment)	X	
Follow-up Questionnaire			X (First timepoint only)	
CollaboRATE			X	
WIWI			X	
DRS			X	
1 year Questionnaire			X (3 rd extended assessment)	
Qualitative interview				X
Digit Span Test				X (Patients only)

Provider assessment	
	Study Enrollment
Screening	X
Informed Consent	X
HIPAA	X
Provider Questionnaire	X

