7.2 Sample Size and Accrual

Our primary objective is to establish content validity of the BWS survey. Based on established guidelines, 7-10 participants are needed to establish content validity of survey items in cognitive interviews.⁴¹⁻⁴³ As we will be stratifying patients for cognitive interviews into 2 groups, we will have 10 participants per stratification to ensure saturation in both.

Based on our prior data, we anticipate that we will have a 3:1 split between patients who value living longer most and those who value another attribute most. Therefore, we will need to recruit at least 40 patients to have 10 patients who value another attribute most to participate in cognitive interviews. Accounting for variability and drop out, we will plan to recruit 50 patients total to be able to recruit 10 patients in this group.

10 clinicians will provide for saturation for qualitative interviews.

This study was not designed to be powered to evaluate secondary endpoints or exploratory endpoints.

We expect to accrue up to 50 patients over the time of the study. We see over 500 new patients with hematologic malignancies per year within the division of hematology.

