7.3.2 Secondary Aims

Patient acceptability:

We will conclude the BWS is acceptable if $\geq 70\%$ of patients (35/50) report that it is acceptable. Hypothesizing 80%, the exact binomial 95% CI will be 66.3-90.0%.

Preliminary efficacy:

We will conclude the tool is potentially efficacious if efficacy (defined as participants answering “moderately effective/very effective” to the question: “How effective was the survey to help you and your doctor choose a treatment that was consistent with your goals?”) is reached in $>50\%$ of patients. Estimating 5-7% missing data from enrollment to initial longitudinal questionnaire (from other PRO assessments in advanced cancer patients^{45,46}) and hypothesizing a rate of 75%, the exact binomial 95% CI will be 60.0-86.6%.

Preliminary completion rates:

Frequencies will be reported at each time point. Completion rate out of the original 50 participants will be reported at each month with exact binomial 95% CIs with reasonable precision, no wider than $\pm 14.5\%$. Reasons for dropout will be summarized as available. Associations of baseline patient characteristics with completion rates will be explored using Wilcoxon Rank sum and Kruskal-Wallis tests.

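### The plan does not settle whether its 50 are patients who consent or patients who complete the survey; under the recruitment rule in 4.3.2, consented non-completers leave the completion-rate denominator

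*Combined protocol and SAP*

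**What the plan says.** All references are to the combined protocol and SAP.

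- **Recruitment rule.** Section 4.3.2 states: "Eligible patients will be sequentially approached to be recruited to this study until 50 patients are recruited who complete BWS survey". The synopsis (1.1) points the same way: "We plan to recruit 50 total patients to complete the survey to ensure adequate recruitment in each group". In 4.3.2 consent comes before the first questionnaires, so a patient can be enrolled without ever completing the BWS.
- **Competing statements.** Section 4.3.1 says: "The study will recruit 50 total participants and conduct qualitative interviews on a subset of 20 participants". Section 7.2 says: "We expect to accrue up to 50 patients over the time of the study". Neither makes completion a condition.
- **Completion endpoint.** Secondary objective 3 in 2.2 gives a count without a denominator: "This will be reported by the number of patients who complete the BWS survey at each timepoint across the study". The denominator appears in 7.3.2: "Completion rate out of the original 50 participants will be reported at each month", with exact binomial intervals said to be no wider than ±14.5%.
- **Late completion.** The Time and Events table (5.1) has an Interim column with a catch-up entry for the BWS, "X (if not completed at enrollment").
- **Feasibility.** The synopsis says: "Secondary outcomes will evaluate acceptability and feasibility of administering the survey". Section 4.3.2 collects refusal reasons from patients who decline the study, partly to judge selection bias and feasibility. It sets no matching rule for patients who consent and never complete.

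**The concern.** If the 50 in 7.3.2 are the 50 completers of 4.3.2, completing the survey is both the condition for being counted and the outcome being counted. This acts as an undeclared run-in. Patients who agreed to take part but could not or did not use the survey are replaced, and the completion rate does not register them.

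At stake is the answer to objective 3 and to the feasibility question in the synopsis, for a tool meant for point-of-care use in older, newly diagnosed patients. Completion of the entry BWS would carry no information. Rates from Longitudinal Assessment 1 onward would describe retention among patients who had already completed once, yet could be read as completion among everyone who consented. The planned tests of baseline characteristics against completion would lose the same patients, who are the most informative ones for that question.

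**Working it through.** **1. Reproduce the plan's figure.** The Clopper-Pearson 95% interval was computed for every count from 0 to 50 with n = 50. The largest half-width is at 25/50: 35.5% to 64.5%, so (64.5 − 35.5)/2 = 14.5 points. This matches 7.3.2 and shows that the planned denominator is 50. The documents do not say which 50.

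**2. Set the two readings side by side.**

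- *50 enrolled in total (4.3.1, 7.2).* Non-completers stay in the denominator and there is no bias, but fewer than 50 may complete the survey.
- *50 completers (4.3.2, 1.1).* Non-completers are replaced, and the number consented, N, exceeds 50 by however many never complete.

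The readings agree only if every consented patient completes.

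**3. Size under the 4.3.2 rule.** Let d be the share of consented patients who never complete the BWS. The documents do not give d, so a range is assumed. Then N = 50/(1 − d), rounded up: 50/0.95 = 52.6, 50/0.93 = 53.8, 50/0.90 = 55.6 and 50/0.80 = 62.5. The count of 40 at a later timepoint is illustrative. Exact 95% intervals, treating N as fixed, are in brackets.

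| Assumed d | N consented | Entry BWS, 50/N | Later count of 40, 40/N |
|---|---|---|---|
| 0% | 50 | 100% (92.9–100) | 80.0% (66.3–90.0) |
| 5% | 53 | 94.3% (84.3–98.8) | 75.5% (61.7–86.2) |
| 7% | 54 | 92.6% (82.1–97.9) | 74.1% (60.3–85.0) |
| 10% | 56 | 89.3% (78.1–96.0) | 71.4% (57.8–82.7) |
| 20% | 63 | 79.4% (67.3–88.5) | 63.5% (50.4–75.3) |

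With the denominator held at 50 completers, the reported figures are those of the first row whatever d is.

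**4. Which assessment is fixed at 100%.** Only ever completing the entry BWS is fixed. Section 7.3.2 expects 5% to 7% missing data between enrollment and the first longitudinal questionnaire, that is 50 × 0.95 = 47.5 to 50 × 0.93 = 46.5 responders. Its interval for preliminary efficacy, 60.0% to 86.6% at a rate of 75%, reproduces with n = 46. So the plan itself expects less than full completion at Longitudinal Assessment 1.

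**The case against.** The strongest reply is that the 50 of 7.3.2 may simply be everyone enrolled. Section 4.3.1 stands directly before the recruitment rule and attaches no completion condition. Section 7.2 caps accrual at 50 and reaches 50 from 40 by allowing for variability and dropout. On that reading non-completers remain in the denominator. This stands as a reason not to call the exclusion certain. It does not clear the plan, because 4.3.2 is the only operational stopping rule and it conflicts with that reading once one consented patient fails to complete.

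A second reply is that completers of the entry survey are a fair denominator for completion over time, and that the endpoint is descriptive, unpowered and without a threshold. This limits the consequence. A rate conditional on one completion is legitimate if it is labelled so, but it does not by itself answer the feasibility question.

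Three stronger readings are tempting and are not supported:

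- *Completion at the first timepoint is 100%.* Table 5.1 uses that term for the first longitudinal assessment, where missing data are expected. Because of the Interim catch-up, even on-time completion at enrollment is not fixed.
- *Consented non-completers are recorded nowhere.* Enrollment is tracked in a database (8.3), accrual is reported to the monitoring committee (8.8), and dropout reasons are summarized where available (7.3.2). What is missing is a rule that brings these patients into the completion rate.
- *Every later rate is certainly inflated.* The Interim column provides for late completion and does not show that patients never complete. The plan also provides training, staff help and calls (4.3.2), so d could be zero.

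**Conclusion.** The point holds as an undefined denominator that the operational rule resolves in the flattering direction. Two steps are certain from the text: the completion denominator is 50, and the sections disagree on whether those are patients enrolled or patients who completed. That the 50 of 7.3.2 are the completers is an inference from 4.3.2 and 1.1.

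If that inference is right, later rates are too high as estimates for all consented patients by the factor N/50. With an assumed d of 5% to 20% and a count of 40, the overstatement is 80.0 − 75.5 = 4.5 to 80.0 − 63.5 = 16.5 percentage points. The 5% and 7% values are borrowed from the plan's missing-data estimate for a different interval; 10% and 20% have no source in the documents.

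No calculation in the plan is wrong. Content validity and the interview sample size are unaffected. The change should be made because it removes the ambiguity at almost no cost.

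**What to change.** 1. In 7.3.2, make all consented patients, including those who never complete the entry BWS, the primary denominator for completion at every timepoint.
2. Report the number consented and the number who completed the entry BWS.
3. Keep the rate out of 50 as a secondary figure, labelled as *among patients who completed the entry BWS*.
4. Include consented non-completers in the completion-association tests where their data exist. Section 4.3.2 has medical-record data recorded upon enrollment, so some baseline characteristics should be available without the questionnaires.
5. Reconcile 1.1, 4.3.1, 4.3.2, 7.2 and 7.3.2 so that 50 is the number of BWS completers and the number consented may exceed it. This keeps the target that the interview groups were sized on.

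The cost is a wording change and a count that enrollment tracking should already hold. The target of 50 completers in 4.3.2 does not change. The stated ±14.5% bound still holds, since a larger denominator narrows the widest interval. The downside is a somewhat lower reported completion rate if any consented patient never completes.
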